### 5.1.3.2 Concomitant medication start date imputation

Rules for imputing the CM start date:

The following table explains the notation used in the logic matrix. Please note that **missing start dates** will not be imputed.

	Day	Month	Year
Partial CMD Start Date	Not used	MON	YYYY
Index Admission Date	Not used	ZHSTM	ZHSTY

Where ZHSTM and ZHSTY is the corresponding Month and Year part of Index Admission Date.

The following matrix explains the logic behind the imputation.

	MON MISSING	MON < ZHSTM	MON = ZHSTM	MON > ZHSTM
YYYY MISSING	( 1 ) Uncertain	( 1 ) Uncertain	( 1 ) Uncertain	( 1 ) Uncertain
YYYY < ZHSTY	( 2.a ) Before Admission Date	( 2.b ) Before Admission Date	( 2.b ) Before Admission Date	( 2.b ) Before Admission Date
YYYY = ZHSTY	( 4.a ) Uncertain	( 4.b ) Before Admission Date	( 4.a ) Uncertain	( 4.c ) After Admission Date
YYYY > ZHSTY	( 3.a ) After Admission Date	( 3.b ) After Admission Date	( 3.b ) After Admission Date	( 3.b ) After Admission Date

1. If the CM start date year value is missing and month/day is not missing, the imputed CM start date is set to one day prior to index admission date.
2. If the CM start date year value is less than the index admission date year value, the CM started before index admission. Therefore:
  - a. If the CM month is missing, the imputed CM start date is set to the mid-year point (01JulYYYY).
  - b. Else if the CM month is not missing, the imputed CM start date is set to the mid-month point (15MONYYYY).
3. If the CM start date year value is greater than the index admission date year value, the CM started after index admission. Therefore:

- a. If the CM month is missing, the imputed CM start date is set to the year start point (01JanYYYY).
  - b. Else if the CM month is not missing, the imputed CM start date is set to the month start point (01MONYYYY).
4. If the CM start date year value is equal to the index admission date year value:
- a. And the CM month is missing or the CM month is equal to the index admission date month, then the imputed CM start date is set to one day prior to index admission date.
  - b. Else if the CM month is less than the index admission date month, the imputed CM start date is set to the mid-month point (15MONYYYY).
  - c. Else if the CM month is greater than the index admission date month, the imputed CM start date is set to the month start point (01MONYYYY).

If complete (imputed) CM end date is available and the imputed CM start date is greater than the (imputed) CM end date, then imputed CM start date should be set to the (imputed) CM end date.

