3.3 Rationale of dose/regimen, route of administration and duration of treatment

Starting dose, target dose, regimen, titration scheme, and tapering-off scheme for LCZ696 all are in accordance with approved product labeling.

The target dose of 200 mg LCZ696 bid used in this protocol is the dose studied in the CLCZ696B2314/PARADIGM-HF trial that demonstrated superiority over enalapril 10 mg bid. A dose of 200 mg LCZ696 bid delivers similar exposures of valsartan (assessed by AUC) as valsartan 160 mg bid, the maximal approved valsartan dose for HF and the dose recommended in international guidelines for the treatment of HF. In addition, biomarker analysis (increase in levels of ANP and cGMP) indicates that this dose delivers approximately 90% of its maximal neprilysin inhibition (Gu J, 2010).

The duration of the Treatment Epoch for 10 weeks after Randomization is deemed adequate to enable the assessment of the study endpoints: number of patients in the Pre-discharge treatment initiation group and number of patients in the Post-discharge treatment initiation

Amended clinical trial protocol v02

group achieving the target dose of 200 mg LCZ696 twice daily, as well as the safety and tolerability of LCZ696 treatment. The Follow-up Epoch for 16 weeks is deemed adequate to evaluate maintenance of either target- or tolerated dose in both treatment groups (Pre- and Post-discharge).

With respect to oral HF treatments, the proportion of patients treated with ACE inhibitors and ARBs, beta-blockers, and mineralocorticoid-receptor-antagonists (MRA) significantly increases at discharge after the index admission. This practice is supporting the event of an admission for HF as an opportunity to optimize the patient's background therapy, for a relevant number of patients (Maggioni A, 2013b). Pre-discharge initiation may be one approach to optimize evidence-based treatments in this population. In the IMPACT-HF study, Pre-discharge initiation of the beta-blocker carvedilol in stabilized patients hospitalized for HF, did not increase side effects or length of stay and was not associated with an increased risk of serious adverse events up to 60 days after discharge (Gattis WA, 2004).

Pre-discharge initiation of LCZ696 is expected to provide patients with the benefits of novel therapeutic approach of simultaneous neprilysin inhibition and angiotensin type 1 (AT₁) receptor blockade as early as possible.

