**Table 2-2 Subgroups to be used in the statistical analysis**

	Subgroup
1	Age groups: (<65, ≥65; <75, ≥75 years)
2	Gender
3	Race (Caucasian, Black, Asian, Other)
4	eGFR (≥ 30 - <60 mL/min/1.73m  , ≥ 60 mL/min/1.73m  )
5	Patients on Beta-blocker before admission (yes, no)
6	Patients on MRA (aldosterone antagonist) before admission (yes, no)
7	Patients on diuretics at baseline (before admission) (yes, no)
8	ACEI or ARBs or Naïve prior to admission (ACEi, ARB, naive)
10	Diabetes (yes, no)
11	History of implantable device (CRT or ICD) (yes, no)
12	Heart failure due to ischemic heart disease (yes, no)
13	Previous hospitalization within 12 months (yes, no)
14	Atrial Fibrillation (present, absent)
15	Systolic BP at baseline (<100, ≥100 - <120, ≥120 mmHg)
16	Region *

\*Region is defined as outlined in Table 2-1

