#### **2.4.2 Prior, concomitant and post therapies**

Prior or concomitant medications will be summarized for the safety set in separate tabulations based on the coding dictionary used. Prior and concomitant medications used during the randomized phase will be summarized by therapeutic class, preferred term and treatment group.

The SAF population will be used for the above analyses.

Prior medications are defined as drugs taken prior to index hospital admission. Concomitant medication is any medication given at least once post-admission and the last day of the study, including those which were started pre-admission and continued post-admission. Prior or concomitant medication will be identified based on recorded or imputed start and end dates of medication taking. Medications administered during the acute treatments of the decompensated heart failure event (from admission to the time of signing ICF) will NOT be included in the CRFs. Concomitant medication at discharge will be summarized separately.

Per protocol, HF-related therapy starting after the End of Study (to ensure adequate chronic treatment after conclusion of study participation) is also reported. This therapy is HF-specific and may start either on the same day of EoS or as late as 10 days later due to availability in the country of the commercial product, and also considering the needed 36-h washout that may be

needed to resume ACEI treatment after ending study medication administration. A separate table will be compiled indicating the treatment started after End of study Visit.

Prior and concomitant heart failure and cardiovascular-related medications will be summarized separately at separate time points. To be consistent with LCZ696B2314, here are the medications that will be summarized:

- ACEi\*
- ARBs\*
- Beta-blocking agents\*
- Diuretic\*
- Loop diuretics
- Thiazide
- Other Potassium sparing diuretics
- Mineralocorticoid receptor antagonists (MRAs)\*
- Digoxin
- Cardiac glycosides\*
- Calcium Channel Blockers (CCB)/Calcium antagonist\*
- Nitrates\*
- Other vasodilators\*
- Oral anticoagulant\*
- Other antiplatelet agents\*
- Aspirin\*
- Antiarrhythmic agent\*
- Statins\*
- Other lipid lowering agents\*
- Simvastatin
- Inotropic agents

Note: those with an asterisk will be included additionally in a figure

The classes of medications will be defined in a separate file with ATC preferred term and WHO drug code.

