### **2.5.2 Statistical hypothesis, model, and method of analysis**

The primary endpoint will be analyzed using the stratified Cochran-Mantel-Haenszel method with treatment group and randomization stratification variable (ACEI stratum, ARB stratum, or naïve patient stratum) as stratification factor; although randomization is stratified at the country level, country will not be used here as an additional stratification factor due to the expected small cell counts in some countries, in particular in the naïve patient stratum. The risk ratio (of the Pre-discharge initiation of LCZ696 arm versus the Post-discharge initiation of LCZ696 arm) will be estimated with a 2-sided 95% CI along with the estimated rate and 95% CI for each treatment arm. The above analyses will be performed based on SAF; patients will be analyzed according to treatment actually received, as well as the actual stratum (rather than randomized stratum).

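### SAP 5.1.3.2 dates partially dated drugs to the day before admission even when they were first recorded after consent, so drugs started after admission are usually counted as prior therapy

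*SAP*

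**What the plan says.** SAP 5.1.3.2 imputes partial start dates of concomitant medication against the index admission date. For a start year equal to the admission year, rule 4a applies if the month is missing, or if "the CM month is equal to the index admission date month, then the imputed CM start date is set to one day prior". Both cases therefore go to the day before admission. The SAP's own logic matrix labels these two cells *Uncertain*. Rule 1 gives the same date when the year is missing but month and day are present. A known later month in the admission year is handled differently: "Else if the CM month is greater than the index admission date month, the imputed CM start date is set to the month start point". A closing check applies if the imputed start falls after the end date: "then imputed CM start date should be set to the (imputed) CM end date". SAP 5.1.3.3 refers prior therapies back to these rules.

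SAP 2.4.2 defines prior medication as drugs taken before the index admission and adds: "Prior or concomitant medication will be identified based on recorded or imputed start and end dates of medication taking".

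SAP Table 2-2 lists subgroups by beta-blocker, MRA, diuretic and ACEI/ARB/naïve status before admission (rows 5 to 8), for example "Patients on diuretics at baseline (before admission) (yes, no"). SAP 2.2.1 applies them to the primary and secondary endpoints in tables and forest plots. SAP 2.5.2 analyses patients by treatment received "as well as the actual stratum (rather than randomized stratum"). Neither place names the data source for these classifications.

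Protocol 5.5.7, 6.2 and the footnotes to Table 6-1 show that medication taken before admission is collected at Screening so that the stratum can be allocated. Protocol 5.5.7 keeps drugs given for the acute event, from admission to consent, out of the CRF.

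**The concern.** The rule settles an uncertain date in one direction only. That default suits a long-standing drug whose start day nobody remembers. It does not suit a drug that first appears in the CRF after consent, and the rule does not separate the two.

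The period it covers is also one in which heart-failure drugs are often started. Protocol 3.3 says that use of ACEI/ARB, beta-blockers and MRA "significantly increases at discharge after the index admission". A drug started then with an incomplete date is likely to be reported as therapy the patient was already taking.

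The prior-medication tables follow the rule directly. If the Table 2-2 flags were built from the same dates, some patients newly started on a class would move into the before-admission *yes* group. If the actual stratum were built from them, a naïve patient given an ACEI or ARB after admission could leave a stratum planned at about 70 patients.

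**Working it through.** The plan gives no rate of partial dates and no misclassification figure, so there is no stated number to reproduce. The check applies the rule as written.

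**1. Worked cases, admission on 3 October 2016**
- Started 10 October, day missing: imputed 2 October, so prior.
- The same with an end date of 5 November: still 2 October. The end-date check can only move a start earlier, so it does not undo rule 4a.
- Started in November, day missing: imputed 1 November, so not prior.
- Started in November, month missing: imputed 2 October, so prior.

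**2. How often a true post-admission start is moved before admission**

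Assumption: admission dates are equally likely over the 730 days from 1 January 2016 to 30 December 2017. The lag k is the number of days from admission to the true start. Protocol 3.1 gives an average stay of about 5-10 days, so these are plausible lags for a start at discharge.

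*Day missing.* The record is moved when the start falls in the admission month. It escapes on the last k dates of each month: 23 full months, plus a December 2017 that lacks its last day.
- k = 5: escapes = 23×5 + 4 = 119; (730 − 119)/730 = 83.7%.
- k = 10: escapes = 23×10 + 9 = 239; (730 − 239)/730 = 67.3%.
- k = 14: escapes = 23×14 + 13 = 335; (730 − 335)/730 = 54.1%.
- k = 28: moved on 3 dates in each of 14 months of 31 days, 2 in each of 8 months of 30 days and 1 in February 2016; 59/730 = 8.1%.

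*Month also missing.* The record is moved when the start falls in the admission year.
- k = 5: (730 − 5 − 4)/730 = 98.8%.
- k = 10: (730 − 10 − 9)/730 = 97.4%.
- k = 70: (730 − 70 − 69)/730 = 81.0%.

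A second window, the 671 dates from 1 March 2016 to 31 December 2017, gives nearly the same results. Day missing: (671 − 22×5)/671 = 83.6% and (671 − 22×10)/671 = 67.2%. Month missing: 98.5% and 97.0%.

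**3. Illustrative number of patients per drug class**

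Moved = N × q × f × h. None of these inputs is in the documents except the naïve target of 70:
- N = 400 of 1000 patients truly not on the class before admission;
- q = 30-50% of them newly started;
- f = share of those records with a partial date;
- h = 75% moved, a value between the 67% and 84% above.

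| f | q = 30% | q = 50% |
|---|---|---|
| 2% | 1.8 | 3.0 |
| 5% | 4.5 | 7.5 |
| 10% | 9 | 15 |
| 20% | 18 | 30 |

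That is about 0.2% to 3% of 1000 patients. For the naïve stratum, with N = 70 and the same q, f and h, the range is about 0.3 (70×0.3×0.02×0.75) to about 5 (70×0.5×0.20×0.75). It applies only if the stratum is derived from imputed dates.

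**The case against.** The strongest reply is that the rule is a pre-specified default for dates the SAP itself calls uncertain, and that it touches little. Much of this stands.

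- Complete dates are unaffected, as is a known later month in the admission year. Drugs given for the acute event before consent are not in the CRF. A reader might infer that every drug started in hospital is relabelled; the documents do not support that. The exposed records are mainly drugs started after consent or at discharge, plus therapy recorded as ongoing at stabilization.
- A reader might infer that the before-admission subgroups and the primary stratum are corrupted. The documents do not show this. No section says that the Table 2-2 flags or the actual stratum use imputed dates, and a separate Screening record exists that could supply them.
- A reader might infer a bias confined to the Post-discharge arm, because those patients stay on ACEI/ARB while awaiting LCZ696. Protocol 3.1 allows Pre-discharge patients up to 7 days from Randomization to first dose. Protocol 5.5.6 lets any patient resume ACEI/ARB after permanent discontinuation, and 5.5.13 records post-study ACEI/ARB for all. Exposure after Randomization is longer in the Post-discharge arm but not limited to it.
- Rule 1 does not act whenever the year is missing. It needs month and day, and wholly missing start dates are not imputed.
- Prior and concomitant are not exclusive. A drug moved to prior still counts as concomitant if it continued after admission.
- The subgroup displays are descriptive, and SAP 5.4.1 performs no statistical test.

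These points limit the reach of the problem. They do not explain why a drug first recorded after consent should be dated before admission when pre-admission drugs are collected separately.

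**Conclusion.** The point holds for the prior-medication tables. A stated rule gives a predictable, one-way wrong classification of partially dated drugs begun after admission: about 84% of the time at a 5-day lag and 67% at 10 days when only the day is missing, falling to about 8% at 28 days, and 97-99% at 5-10 days when the month is missing too. These shares are conditional on a partial date and assume evenly spread admissions.

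For Table 2-2 rows 5 to 8 and the actual stratum, the finding is a gap. Misclassification is possible if they use the same dates, and the SAP should say whether they do. The number of patients is probably small: about 2 to 30 per drug class if 2-20% of the relevant dates are partial, on the assumptions shown. The change is worth making because the rule errs systematically and the information needed to avoid it is already collected.

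**What to change.** 1. In SAP 2.2.1, 2.4.2 and 2.5.2, state that before-admission status (prior-medication tables and Table 2-2 rows 5 to 8) and the actual stratum come from the Visit 1 record of pre-admission medication collected for stratification, not from imputed dates.
2. In SAP 5.1.3.2, limit the day-before-admission imputation in rules 1 and 4a to drugs reported in that record.
3. For drugs first recorded after consent that would otherwise fall under rules 1 or 4a, impute the later of the consent date and the first day of the known month. Use the consent date when the month or the year is unknown. Cap the result at the recorded end date.

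The cost is a small programming change with no new data. The drawback is that a long-standing drug omitted at Visit 1 would be dated after consent, an error in the other direction. A count of partial start dates by drug class and arm would show whether either error matters.

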### **5.1.3.3 Prior therapies date imputation**

See above

### **5.1.3.4 Post therapies date imputation**

See above

### **5.1.3.5 Other imputations**

There are currently no other imputation rules.

## **5.1.4 Medical history date imputation**

If the date is not known or is incomplete, the imputation rules are:

1. If only the day is unknown, then the 01th day of this month will be imputed for a missing day;
2. If only the month is unknown, then July will be used for imputation of the missing;
3. If only the year is known, then the 1st of Jan. will be imputed for a missing day and month
4. If AE year is missing or AE is ongoing, the end date will not be imputed.

## **5.2 The imputed medical history date cannot be later than the screening date.AEs coding/grading**

Adverse events will be coded using the Medical Dictionary for Regulatory Activities (MedDRA) version available at database lock.

### 5.3 Laboratory parameters derivations

See section 2.8.3.

### 5.4 Statistical models

#### 5.4.1 Primary analysis

The primary endpoint will be analyzed using the stratified Cochran-Mantel-Haenszel method with treatment group and randomization stratification variable (ACEI stratum, ARB stratum, or naïve patient stratum) as stratification factor; although randomization is stratified at the country level, country will not be used here as an additional stratification factor due to the expected small cell counts in some countries, in particular in the naïve patient stratum. The risk ratio (of the Pre-discharge initiation of LCZ696 arm versus the Post-discharge initiation of LCZ696 arm) will be estimated with a 2-sided 95% CI along with the estimated rate and 95% CI for each treatment arm; no statistical test will be performed. The above analyses will be performed based on SAF.

For a single 2 x 2 table within each stratum, the layout is

Treatment	Outcome present	Outcome Absent	Total
Post-discharge	A	b	a+b
Pre-discharge	C	d	c+d
Total	a+c	b+d	n

The risk ratio  $\widehat{RR}_{\text{post vs pre}} = (a/(a + b))/(c/(c + d))$

The Cochran-Mantel-Haenzel (CMH) test is for a series of two-by-two tables, one for each stratum, and the risk ratio estimate is

$$\widehat{RR}_{CMH} = \frac{\sum \frac{a_i (c_i + d_i)}{n_i}}{\sum \frac{c_i (a_i + b_i)}{n_i}}$$

PROC FREQ is used to calculate the relative risk estimate and the 95% confidence interval, using the RELRISK option (Dmitrienko et al, 2005).

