## 2.2.1 Subgroup of interest

Here is a list of subgroups to be used in the analysis. They will be summarized descriptively. They will also be used to stratify the primary and secondary endpoint analyses both in descriptive tables, as well as graphically in forest plots.

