## 2.8 Safety analyses

The following secondary variables will be used in the analyses:

- Achieving and maintaining either the dose of 100 mg and/or 200 mg LCZ696 bid for at least 2 weeks leading to week 10 after randomization, regardless of previous dose interruption or down-titration during the 10-week after Randomization (Yes/no)
- Achieving and maintaining any dose of LCZ696 for at least 2 weeks leading to week 10 after randomization, regardless of previous dose interruption or down-titration during the 10-week after Randomization (Yes/no)
- Permanently discontinuation from study drug (Yes/no) at any time between Randomization and week-10 after randomization due to Adverse Events

These secondary variables will be analyzed in an identical fashion to the primary variable (using the stratified Cochran-Mantel-Haenszel method; see 2.5.2 for details).

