### 3 Sample size calculation

The purpose of this study is to explore two modalities (Pre-discharge, and Post-discharge) of treatment initiation with LCZ696 in HFrEF patients following stabilization after an ADHF episode.

A sample size of about 1000 patients provides reasonable precision across a range of possible outcomes. When the observed rate of 10-weeks up-titration treatment success is 80% in both pre- and post-discharge, it will provide estimated risk-ratio and 95% CI of 1.00 (0.94, 1.06).

Observed rate of up-titration success at week 10 after Randomization		Risk ratio (Pre-discharge / Post-discharge)	2-sided 95% CI	Total sample size without adjustment
Late initiation	Early initiation			
75%	70%	0.93	0.87, 1.01	1000
75%	75%	1.00	0.93, 1.07	1000
75%	80%	1.07	1.00, 1.14	1000
80%	75%	0.94	0.88, 1.00	1000
80%	80%	1.00	0.94, 1.06	1000
80%	85%	1.06	1.00, 1.13	1000

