#### 5.4.2 Key secondary analysis

The three secondary endpoints are analyzed in identical fashion to the primary analysis, defined in section 5.4.1.

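### SAP 5.4.1 defines the primary risk ratio as Pre-discharge over Post-discharge, but its 2×2 layout, label and Mantel-Haenszel formula compute Post-discharge over Pre-discharge

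*SAP*

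**What the plan says.** The direction is stated in words in SAP 5.4.1: "The risk ratio (of the Pre-discharge initiation of LCZ696 arm versus the Post-discharge initiation of LCZ696 arm) will be estimated". Protocol 9.4.2 and SAP 2.5.2 carry the same definition, and the Protocol summary agrees. The sample size tables in Protocol 9.7 and SAP 3 head the relevant column "Risk ratio (Pre-discharge / Post-discharge".

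The specification further down SAP 5.4.1 has three parts:

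- a 2×2 layout with Post-discharge in the first row (cells a, b) and Pre-discharge in the second (cells c, d);
- a single-table ratio whose subscript and formula read "post vs pre}} = (a/(a + b))/(c/(c + d" (the closing brackets fall outside the quote);
- a stratified estimator with Σ aᵢ(cᵢ+dᵢ)/nᵢ over Σ cᵢ(aᵢ+bᵢ)/nᵢ.

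The software is then named: "PROC FREQ is used to calculate the relative risk estimate and the 95% confidence interval, using the RELRISK option". No row order or treatment coding is given.

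The secondary endpoints are referred to two places. SAP 2.8 has them analysed "using the stratified Cochran-Mantel-Haenszel method; see 2.5.2 for details", and SAP 5.4.2 says "The three secondary endpoints are analyzed in identical fashion to the primary analysis, defined in section 5.4.1". On the subgroups, SAP 2.2.1 says: "They will also be used to stratify the primary and secondary endpoint analyses both in descriptive tables, as well as graphically in forest plots".

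**The concern.** One section gives two directions for the primary estimate. SAP 4, which lists departures from the protocol's analyses, records no change of direction, and no sentence says that the computed ratio will be inverted before reporting.

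SAP 5.4.1 is the only place where the calculation is written out, and SAP 2.1 gives the analysis to an external vendor. Someone working from the formula block computes Post/Pre; someone working from SAP 2.5.2 computes Pre/Post. Both can say that they followed the SAP. If the first result is placed under a Pre/Post heading, the estimate appears to favour the wrong arm.

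Because no hypothesis test is planned, the risk ratio and its interval are the main between-arm result, so their direction matters. The secondary risk ratios are exposed through SAP 5.4.2. They mix favourable outcomes (dose maintained) with an unfavourable one (discontinuation for adverse events), so a reversal would be hard to spot from the sign alone. Subgroup forest plots would be exposed too if they reuse the same calculation.

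**Working it through.** **Inputs.** N = 1000 (SAP 3) and 1:1 allocation (SAP 1.1) give 500 per arm. Success rates come from the SAP 3 table, where late initiation is Post-discharge and early initiation is Pre-discharge. Intervals are two-sided 95%.

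**Step 1: reproduce the plan's table.** For rates p₁ (numerator arm) and p₂ (denominator arm):

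RR = p₁/p₂; SE(log RR) = √[(1−p₁)/(500p₁) + (1−p₂)/(500p₂)]; CI = RR × exp(±1.96 SE).

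| Post | Pre | Printed in SAP 3 | Computed Pre/Post | Computed Post/Pre |
|---|---|---|---|---|
| 75% | 70% | 0.93 (0.87, 1.01) | 0.933 (0.865, 1.008) | 1.071 (0.993, 1.157) |
| 75% | 75% | 1.00 (0.93, 1.07) | 1.000 (0.931, 1.074) | 1.000 (0.931, 1.074) |
| 75% | 80% | 1.07 (1.00, 1.14) | 1.067 (0.998, 1.141) | 0.938 (0.877, 1.002) |
| 80% | 75% | 0.94 (0.88, 1.00) | 0.938 (0.877, 1.002) | 1.067 (0.998, 1.141) |
| 80% | 80% | 1.00 (0.94, 1.06) | 1.000 (0.940, 1.064) | 1.000 (0.940, 1.064) |
| 80% | 85% | 1.06 (1.00, 1.13) | 1.063 (1.003, 1.125) | 0.941 (0.889, 0.997) |

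Pre/Post reproduces every printed risk ratio. The only mismatch is the lower limit in the first row (0.8646 against a printed 0.87), a rounding-level difference with no bearing on direction. In the four rows with unequal rates, Post/Pre does not reproduce the printed ratios. The equal-rate rows, including the 80/80 case that the SAP highlights, are the same either way, so checking a program against them cannot show a reversal.

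**Step 2: apply the printed stratified formula.** The documents give about 930 ACEI or ARB patients and about 70 naïve patients. The ACEI/ARB split is an assumption: 300 ACEI, 165 ARB and 35 naïve per arm, with the same rates in every stratum. Take Post 80% and Pre 85%.

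- Layout as printed: a = 240, 132, 28 (Post successes); c = 255, 140.25, 29.75 (Pre successes, expected counts); n = 600, 330, 70.
- Numerator: 240×300/600 + 132×165/330 + 28×35/70 = 120 + 66 + 14 = 200.
- Denominator: 255×300/600 + 140.25×165/330 + 29.75×35/70 = 127.5 + 70.125 + 14.875 = 212.5.
- As printed: 200/212.5 = 0.941, CI (0.889, 0.997) with the Greenland-Robins variance.
- Rows swapped: 212.5/200 = 1.063, CI (1.003, 1.125).

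For Post 75% and Pre 80%, the printed layout gives 0.938 (0.877, 1.002) and the swapped rows give 1.067 (0.998, 1.141). This pair is the same under assumed ACEI/ARB splits per arm of 330/135, 300/165 and 232.5/232.5.

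**Step 3: what changes and what does not.** The two directions are exact reciprocals with their limits inverted and exchanged. The standard error on the log scale is the same for both: √(0.000667 + 0.000500) = 0.0342 for 75/80, and √(0.000500 + 0.000353) = 0.0292 for 80/85. An interval that excludes 1 in one direction excludes it in the other.

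**The case against.** The strongest reply is that the intended direction is not in doubt. It is stated consistently in the Protocol summary, Protocol 9.4.2 and 9.7, SAP 2.5.2 and 3, and the text of SAP 5.4.1, so the algebra in the appendix is a lone editorial slip. Harm needs two errors together: the block must be programmed as printed, and its explicit label must then be lost. The same section requires the rate in each arm beside the ratio, so a Pre/Post ratio of 0.94 next to 80% Post and 85% Pre would look wrong. The trial is exploratory, with no test and no decision rule, and the listed interim reviews contain no risk ratio. No printed number is wrong, and the formula is correct for its own layout and label.

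Most of this stands, and it limits the consequence. It does not remove the contradiction: the only written calculation yields the reciprocal of the stated estimand, and the PROC FREQ sentence does not settle the order.

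Two further points are fair. The double reference for the secondary endpoints is not a separate defect, since both targets agree once SAP 5.4.1 is corrected. SAP 2.2.1 names no formula, so the exposure of the forest plots is an inference.

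**Conclusion.** The concern holds. Layout, label and Mantel-Haenszel formula in SAP 5.4.1 agree with one another and contradict the text of that section and every other statement of the estimand. Because the three agree, damage in text extraction is not a plausible explanation. The formula block is the outlier.

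The size is a reciprocal: for Post 80% and Pre 85%, an interval wholly above 1 becomes one wholly below 1. Precision, arm rates and exclusion of 1 are unchanged. The figures assume 500 per arm and large-sample intervals, and the stratified runs also assume equal rates across strata and an ACEI/ARB split. The reversal itself depends on none of these assumptions.

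This is an ambiguous specification of the primary estimate, not evidence of a wrong reported result. The documents do not show what was programmed, and the table shells mentioned in SAP 1 are not shown.

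**What to change.** In SAP 5.4.1, put Pre-discharge in the first row (a, b) and Post-discharge in the second (c, d), relabel the ratio as *pre vs post*, and leave the formulas as they are. They then give Pre/Post and match the SAP 3 table. State the PROC FREQ row order and treatment coding once, and say that it applies to the primary, secondary and subgroup risk ratios. As a tidy-up, have SAP 2.8 and 5.4.2 refer to the same section.

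Verify any program on a row with unequal rates: Post 80% and Pre 85% should return 1.06, not 0.94.

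The change to the plan is wording only. If programs or outputs already exist, their direction should be checked at the same time.
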